7.4.6 Data Handling

Generally, reactogenicity events recorded in the Subject Diary and (unsolicited) AEs recorded in the AE log will be summarized separately. A reactogenicity event will not be recorded as an (unsolicited) AE unless it meets the criteria of an SAE. Any event found in the AE log that is also captured in the Subject Diary will not be counted as an AE to avoid duplication.

Unscheduled or repeated laboratory results will not be analyzed for the summary of continuous values but may be included in the lab shift tables (see Section 8.5.3). Repeated tests will be included only if they reflect abnormal (low or high) results and the corresponding original results are normal. Repeat vital signs will not be analyzed for the summary of continuous values.

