
 To describe the safety profile of NasoVAX in healthy adults when administered by intranasal spray at a single dose of 1×10^9, 1×10^{10}, or 1×10^{11} viral particles (vp) 	
 Reactogenicity: counts and percentages of subjects with local events (nasal irritation, sneezing, nasal congestion, cough, sore throat, change in smell, change in taste, change in vision, eye pain) and systemic events (headache, fatigue, muscle ache, nausea, vomiting, diarrhea, chills, fever) for 14 days after vaccination Adverse Events (AEs): counts and percentages of subjects with AEs from Day 1 to Day 29; medically attended adverse events (MAEs), serious adverse events (SAEs), new-onset chronic illness (NCI) from Day 1 to Day 181
Secondary Objective	

 To evaluate the humoral immune response to NasoVAX when administered by intranasal spray at a single dose of 1×10^9, 1×10^{10}, or 1×10^{11} vp 	
 Antibody level measured by hemagglutination inhibition (HAI) in serum: 
 Geometric mean titer (GMT): the antilog of the mean of the log-transformed titers Geometric mean ratio (GMR): the ratio of postvaccination and prevaccination GMTs within the same dose group Seroprotection rate (SPR): the percentage of subjects with a HAI titer $\geq 1:40$ Seroconversion rate (SCR): the percentage of subjects with either a baseline HAI titer $< 1:10$ and a postvaccination titer $\geq 1:40$ (which is 4 times the assay lower limit of quantitation), or a baseline HAI titer $\geq 1:10$ and a 4-fold increase in postvaccination HAI titer relative to baseline Antibody level measured by microneutralization (MN) in serum: 
 GMT Responder rate: the proportion of subjects with 2-fold and 4-fold rise since baseline

OBJECTIVES	ENDPOINTS
Exploratory Objectives	

 To evaluate the cellular immune response to NasoVAX when administered by intranasal spray at a single dose of 1×10^9, 1×10^{10}, or 1×10^{11} vp 	
 Spot-forming units (SFUs) to hemagglutinin (HA) peptides measured by enzyme-linked immunosorbent spot assay (ELISpot) in peripheral blood mononuclear cells (PBMCs): 
 Geometric mean SFUs Responder rate: the number and percentage of subjects with 3-fold rise since baseline and 25 SFU/million cells greater than baseline

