6.4 Safety Variables

Safety assessments, some of which are listed as endpoints, include the following:

- Reactogenicity (local events, systemic events, and oral temperature)
- AEs and SAEs (events not already included in reactogenicity)
- Safety laboratory tests (hematology, serum chemistry, urinalysis)
- Vital signs (blood pressure, heart rate, body temperature)
- ECG
- Nasopharyngeal swabs for vector shedding
- Viral culture
- Concomitant medications
- Physical exam

7 Statistical Methodology

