7.4.5 Derived Variables

- Non Treatment Emergent Adverse Events include all AEs that stopped the day prior to the vaccination, or started prior to the vaccination but did not increase in severity or relationship during treatment.
- Treatment Emergent Adverse Events (TEAEs) include all AEs that start on or after vaccination, or AEs that are present prior to vaccination, but their severity or relationship increases after the vaccination date
- Change from baseline will be calculated as the observed value at the current visit or time point minus the observed value at baseline.
- Prior medications include all medications that have a start date prior to the date of vaccination.
- Concomitant medications include all medications that are taken on or after the date of vaccination.

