8.5.1 Reactogenicity

Each ALT-103-201 subject will be provided with a diary and a thermometer after each dose. The subjects will record and provide severity grades (Grade 1 – 4) for the following items in a diary daily for the first 14 days after vaccination.

- Local events: nasal irritation, sneezing, nasal congestion, cough, sore throat, change in smell, change in taste, change in vision, eye pain
- Systemic events: headache, fatigue, muscle ache, nausea, vomiting, diarrhea, chills, oral temperature

Oral temperature will be converted to a severity grade using the FDA toxicity grading scale [1].

A cumulative summary of the number and percentage of subjects experiencing at least one reactogenicity event within 14 days after vaccination for each symptom type (local, systemic, temperature, and overall) will be tabulated by maximum severity and dose group. Differences between each NasoVAX dose group and placebo for cumulative symptoms (local, systemic, and overall) will be tested using Kruskal-Wallis tests. The number and percentage of subjects experiencing at least one Grade 3 or 4 reactogenicity event within 14 days after vaccination for each symptom type, as well as 95% Clopper-Pearson exact CIs, will be presented by dose group.

A summary of the number and percentage of subjects experiencing at least one reactogenicity event within 14 days after vaccination will also be tabulated by event

type, maximum severity, and dose group. In addition, a descriptive summary of the duration of symptoms (regardless of severity) will be tabulated by event and dose group.

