8.5.2 Adverse Events

The number and percent of ALT-103-201 subjects with any TEAEs will be displayed by SOC and PT for each dose group. Within each PT, subjects will be counted only once if they had more than one event reported during the treatment period.

The number and percentage of subjects with any TEAE will be presented as well as the corresponding 95% Clopper-Pearson exact CI of the percentage.

For MedDRA SOC, the number and percentage of subjects experiencing at least one TEAE overall and at least one TEAE for a system will be tabulated by severity grade (Grades 1-4) and dose group. For MedDRA PT, the number and percentage of subjects reporting at least one TEAE within a PT category will be tabulated by relationship to study products and dose group. For the calculations in these tables, each subject's TEAEs will be counted once under the maximum severity or the strongest recorded causal relationship to study product.

Summaries will be generated for all serious TEAEs, TEAEs resulting in dose withdrawal, treatment emergent MAEs, and treatment emergent NCI, by SOC and PT for each dose group.

A listing will be produced for all subjects who reported serious TEAEs. The listing will provide details of the events including severity, relationship to study product, time between onset and last study treatment administration, and a summary of the event.

All TEAEs and non-treatment emergent AEs will be listed individually by subject.

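### SAP 7.4.6 (ALT-103-201): the rule keeping diary events out of the AE counts has no exception for serious events, so a serious solicited reaction could be missing from the serious-TEAE outputs

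*SAP*

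**What the plan says.** All of this concerns ALT-103-201. SAP 8.5 restricts the safety analyses to that study, so ALT-FLZ-401 is not touched.

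- **Recording rule, SAP 7.4.6:** "A reactogenicity event will not be recorded as an (unsolicited) AE unless it meets the criteria of an SAE".
- **Counting rule, next sentence of 7.4.6:** "Any event found in the AE log that is also captured in the Subject Diary will not be counted as an AE". The sentence ends by giving avoidance of duplication as its purpose.
- **Safety variables, SAP 6.4:** the relevant list item begins "AEs and SAEs (events not already included in reactogenicity".
- **TEAE definition, SAP 7.4.5:** "Treatment Emergent Adverse Events (TEAEs) include all AEs that start on or after vaccination", plus AEs already present that worsen after vaccination.
- **Planned outputs, SAP 8.5.2:** "Summaries will be generated for all serious TEAEs, TEAEs resulting in dose withdrawal, treatment emergent MAEs, and treatment emergent NCI", and also "A listing will be produced for all subjects who reported serious TEAEs".
- **Primary endpoint, SAP Section 3:** besides AEs to Day 29, it covers "medically attended adverse events (MAEs), serious adverse events (SAEs), new-onset chronic illness (NCI) from Day 1 to Day 181".

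**The concern.** Under the recording rule, the only solicited reactions that properly reach the AE log are serious ones. The counting rule then applies to every log event that is also in the diary. If sites follow the first rule, the events that the second rule removes are the serious ones the first rule let in.

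At stake is the completeness of the serious-TEAE outputs, which report part of the primary safety endpoint. The affected event would still contribute to the reactogenicity tables, but SAP 8.5.1 plans those by maximum grade and says that "a descriptive summary of the duration of symptoms (regardless of severity) will be tabulated by event and dose group". Neither display shows whether an event was serious. The Day 29 interim analysis in SAP 7.3 includes AE summaries, and the 14-day diary period lies wholly before it, so the same wording governs the interim tables.

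**Working it through.** The point rests on how the sections combine, so the main check is a trace of one hypothetical event: a solicited symptom within 14 days of dosing, entered in the diary, that meets SAE criteria.

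1. **7.4.6, recording:** the event goes into the AE log, because it is serious.
2. **7.4.6, counting:** the event is in the log and in the diary, so it is not counted as an AE. The word 'Generally' at the start of the paragraph qualifies only the statement that diary events and AEs are summarized separately; it does not soften this rule.
3. **6.4:** the item names SAEs together with AEs and excludes what reactogenicity already covers. It does not restore the event.
4. **7.4.5:** TEAEs are drawn from AEs. An event not counted as an AE is therefore not counted as a TEAE.
5. **10.1:** the event is absent from Table 14.3.2.2 (TEAEs by SOC and PT), Table 14.3.2.5 (serious TEAEs) and Listing 14.3.2.9 (serious TEAEs).
6. **8.5.2 and Section 3:** these call for all serious TEAEs, all subjects reporting them, and SAEs from Day 1 to Day 181. The result of step 5 does not meet that.

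**Size.** Table 4-1 plans 15 NasoVAX subjects per dose and 45 in total. One affected subject changes the serious-TEAE table by:

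- 1/15 = 6.7% in a dose group;
- 1/45 = 2.2% across all NasoVAX subjects.

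The percentage with any TEAE, and its planned Clopper-Pearson interval, would change only if this event was the subject's sole TEAE. With no affected subject, no table changes.

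**The SAP's own figures for 45 subjects.** SAP 7.1 gives two, and both reproduce:

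- Probability of at least one AE at a 3.6% rate: 1 − (1 − 0.036)^45 = 0.808, against a stated 80%.
- One-sided 90% upper bound on the SAE rate with no SAEs: 1 − 0.10^(1/45) = 4.99%, against a stated 5%.

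Only the second depends on the SAE count. As an illustration with an assumed count, one SAE in 45 gives an exact one-sided 90% upper bound of 8.37% (the 0.90 quantile of a beta distribution with parameters 2 and 44).

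**The case against.** The strongest reply is that the counting sentence is only a clean-up rule. Its stated purpose is to prevent duplication, and it follows a rule that keeps non-serious diary events out of the log. Its natural target is therefore a non-serious reaction logged by mistake. Applying it to SAEs would leave the SAE exception with almost no effect on the counts. Section 8.5.2 twice refers to all serious TEAEs or all subjects who reported them, which also shows what was meant. The 6.4 item is a short description in a list, not a counting rule. The shells and programming notes are a separate document (SAP 10.2) that was not available, and they may already handle the case.

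Much of this stands: keeping SAEs is the probable intent, and 6.4 should not carry much weight alone. But the sentence covers any event, and no available text limits it. A programmer who applies it as written would drop the SAE.

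A reader might infer more than the documents support:

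- **That 7.4.6 contradicts itself.** Recording and counting are different acts, so both sentences can be obeyed. The real conflict is between the counting rule and 8.5.2 with Section 3.
- **That an SAE would vanish from the report or escape oversight.** SAP 7.4 puts all collected data in listings, and under SAP Section 4 a related SAE triggers committee review independently of these tables.
- **That medically attended reactions are wrongly dropped from Table 14.3.2.7.** Under the recording rule, a non-serious diary reaction is not logged as an AE at all. Whether it should count as medically attended depends on a definition in the ALT-103-201 protocol, which was not available.
- **That the 5% bound in 7.1 would be reported wrongly.** That bound is a planning approximation; 8.5.2 plans an interval for any TEAE, not for SAEs.

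**Conclusion.** The point holds as a missing exception in a stated counting rule. Followed literally, SAP 7.4.6 can leave a serious solicited reaction out of Tables 14.3.2.2 and 14.3.2.5 and Listing 14.3.2.9, contrary to 8.5.2 and the primary endpoint in Section 3. Nothing in the available text restores it.

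The effect is narrow. It needs a solicited symptom within the 14-day diary period that meets SAE criteria and appears in both diary and log. The number of such subjects is unknown and may be zero. The percentages above assume the planned group sizes and one affected subject. The conclusion concerns the SAP wording; whether any output would actually be wrong also depends on the programming notes and the ALT-103-201 protocol, neither of which could be checked. Because a primary safety count is involved and the correction is small, it should be made before the tables are run.

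**What to change.** 1. In 7.4.6, limit the counting sentence to non-serious events. Add that events meeting SAE criteria are counted in all AE and serious-TEAE tables and listings even when they are also in the diary.
2. In 6.4, change the item to: *AEs (non-serious events not already included in reactogenicity) and all SAEs*.
3. Footnote the affected tables to say that a serious solicited reaction may appear in both the reactogenicity and the AE displays.
4. Check that the shells and programming notes apply the same rule.

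The cost is two wording changes, one programming condition and a footnote, with no new data collection. The drawback is that an affected event is shown in two places, which the footnote explains. De-duplication of non-serious events is unchanged.

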3	1×10^{11}	15	5
Study Total Target		45	15
Total		60	

A sentinel group of 5 subjects from each cohort will be dosed. Dosing of the remainder of each cohort may proceed after the last sentinel subject completes Day 8 if no events meeting stopping criteria have occurred. The Safety Review Committee (SRC), consisting of the Investigator, the Medical Monitor, and a Sponsor Representative, will review AE, reactogenicity, and laboratory data through at least Day 8 for all subjects in each cohort before subjects are randomized to the next higher dose. If any event meeting stopping criteria occur, the SRC will review all available safety information before additional patients are dosed. Stopping criteria are as follows, using the Food and Drug Administration (FDA) toxicity grading scale [1]:

- Occurrence of any related SAE or Grade 4 AE
- Occurrence of 2 Grade 3 AEs in the same organ system
- Occurrence of the same Grade 3 laboratory abnormality in 2 or more subjects

Each subject will record local events, systemic events, and oral temperature in a diary daily for 14 days after the NasoVAX/placebo dose. Each subject will be contacted by telephone on Day 2 for safety assessment and review of the diary. Subjects will return to the investigational site on Days 4, 8, 15, 29, 91, and 181 for safety and immunogenicity assessments.

A serum sample will be collected from each subject for evaluation of influenza HAI assay against A/California/04/2009 predose on Day 1 on Days 4, 8, 15, 29, 91, and 181; Ad5 antibody, MN assay against both A/California/04/2009(H1N1) and nonrepresented strains, and HAI against nonrepresented strains will also be evaluated at Days 1 and 29. A whole

blood sample will be collected from each subject and processed to isolate PBMCs for evaluation of T-cell responses by ELISpot predose on Day 1 and on Day 8.

A nasopharyngeal swab sample will be collected from each subject at Screening and on Days 4, 8, 15, 29, and 91 to measure concentration of the Ad5 vector for assessment of vaccine vector shedding by quantitative polymerase chain reaction (qPCR) assay. Once a negative result is obtained, later samples may not be tested. ELISA for measurement of IgA will also be performed on the swab samples from Screening and Day 29 for evaluation of mucosal immune response.

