7.4 Analysis of the Study

All statistical tests will be two-sided and a difference resulting in a p-value of less than or equal to 0.05 will be considered statistically significant. All p-values will be rounded to and displayed in four decimals. If a p-value less than 0.0001 occurs it will be shown in tables as <0.0001.

There will be no multiplicity adjustments.

To integrate the 2 studies for the immunogenicity tables, figures, and listings (TFL), subjects enrolled in ALT-FLZ-401 will be treated as an additional arm in the ALT-103-201 study. ALT-FLZ-401 subjects will be denoted as "Fluzone" subjects in the TFL, while ALT-103-201 will be denoted as "NasoVAX" if they are assigned to an active dose, or placebo if appropriate.

Descriptive summaries of variables will be provided where appropriate. Continuous variables will be presented for each dose group by geometric means and 95% confidence intervals (CIs) for the immunogenicity endpoints and by summary statistics (e.g., mean, and standard deviation [SD], median, minimum, and maximum) for other endpoints. Categorical variables will be presented by frequency distributions (including percentages and 95% CIs) for the immunogenicity endpoints and frequency counts and percentages for other endpoints. Expansion of descriptive table categories within each dose group may occur if such elaborations are thought to be useful.

All collected data will be presented in listings. Data not subject to analysis according to this plan will not appear in any tables or graphs but will be included in the data listings.

Post-hoc exploratory analyses not identified in this SAP may be performed to further examine the study data. These analyses will be clearly identified as such in the final clinical study report.

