8.5 Safety Analysis

All safety analyses will be conducted on the Safety Population, and will be performed for ALT-103-201 only. Summaries will be completed by dose group and overall for subjects on an active NasoVAX dose.

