8.5.3 Safety Laboratory Tests

Safety laboratory results for ALT-103-201 subjects will be summarized descriptively for each parameter with continuous values and dose group by visit for the observed value as well as for the change from baseline value. In addition, laboratory shift tables will be provided for all laboratory parameters where grades can be ascertained.

The following safety laboratory parameters will be collected for ALT-103-201 subjects:

- Hematology: hemoglobin, platelet count, white blood cell count with differential (absolute or percent counts of neutrophils, lymphocytes, monocytes, basophils, eosinophils)
- Serum chemistry: alkaline phosphatase, alanine aminotransferase (ALT), aspartate aminotransferase (AST), bicarbonate, bilirubin, chloride, creatine kinase, creatinine, glucose, potassium, sodium, urea nitrogen

- Urinalysis: glucose, protein

Any laboratory abnormality deemed clinically significant by the Investigator will be recorded as an AE.

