10.1 List of Tables, Figures, and Listings

Table No.	Description of Table	Population
14.1.1	Subject Disposition	All Subjects
14.1.2.1	Demographics and Baseline Characteristics	Safety
14.1.2.2	Demographics and Baseline Characteristics	ITT
14.1.2.3	Demographics and Baseline Characteristics	Per-protocol
14.1.3	Medical/Surgical History	Safety
14.2.1	Concomitant Medications	Safety
14.2.2	Concomitant Medications Started Prior to Study Treatment	Safety
14.3.1.1	Summary and Analysis of Worst Reactogenicity Events by Grade	Safety
14.3.1.2	Summary of Worst Reactogenicity Events by Event Type and Grade	Safety
14.3.1.3	Summary of Duration of Reactogenicity Events by Event Type	Safety
14.3.2.1	Overall Summary of Adverse Events	Safety
14.3.2.2	Treatment Emergent Adverse Events (TEAE) by System Organ Class and Preferred Term	Safety
14.3.2.3	Treatment Emergent Adverse Events (TEAE) by System Organ Class and Severity	Safety
14.3.2.4	Treatment Emergent Adverse Events (TEAE) by Preferred Term and Relationship to Study Treatment	Safety
14.3.2.5	Serious Treatment Emergent Adverse Events (TEAE) by System Organ Class and Preferred Term	Safety
14.3.2.6	Treatment Emergent Adverse Events (TEAE) Resulting in Dose Withdrawal by System Organ Class and Preferred Term	Safety
14.3.2.7	Treatment Emergent Medically Attended Adverse Events (MAE) by System Organ Class and Preferred Term	Safety
14.3.2.8	Treatment Emergent New-onset Chronic Illnesses (NCI) by System Organ Class and Preferred Term	Safety
14.3.2.9	Listing of Serious Treatment Emergent Adverse Events	Safety
14.3.3.1	Change from Baseline in Hematology Parameters by Visit	Safety
14.3.3.2	Change from Baseline in Chemistry Parameters by Visit	Safety
14.3.3.3	Shift from Baseline in Hematology Parameters Utilizing Toxicity Grade by Visit	Safety
14.3.3.4	Shift from Baseline in Serum Chemistry Parameters Utilizing Toxicity Grade by Visit	Safety
14.3.3.5	Shift from Baseline in Urinalysis Parameters Utilizing Toxicity Grade by Visit	Safety
14.3.4	Change from Baseline in Vital Sign Parameters by Visit	Safety
14.3.5	Summary of Ad5 Vector Shedding by qPCR of Nasopharyngeal Swabs (copies/5µl) by Visit	Safety
14.3.6.1	Change from Baseline in ECG Parameters by Visit	Safety
14.3.6.2	Shift from Baseline in ECG Overall Interpretation at Day 29	Safety
14.4.1.1	Summary and Analysis of A/California 2009 Antibody Level Measured by HAI in Serum by Visit	Per-protocol

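### The SAP's normal/abnormal test for repeat laboratory results drops higher-grade repeats of already abnormal values from shift tables that are graded by toxicity

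*SAP*

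**What the plan says.** SAP 7.4.6 (Data Handling) first sets where extra laboratory results may go: "Unscheduled or repeated laboratory results will not be analyzed for the summary of continuous values but may be included in the lab shift tables". It then narrows this for repeats: "Repeated tests will be included only if they reflect abnormal (low or high) results and the corresponding original results are normal".

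SAP 8.5.3 defines the tables concerned: "laboratory shift tables will be provided for all laboratory parameters where grades can be ascertained". The table list in SAP 10.1 confirms the scale. Table 14.3.3.3 is titled "Shift from Baseline in Hematology Parameters Utilizing Toxicity Grade by Visit", and Tables 14.3.3.4 (serum chemistry) and 14.3.3.5 (urinalysis) have matching titles.

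Three other provisions bear on the point:

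- Scope, SAP 8.5: "All safety analyses will be conducted on the Safety Population, and will be performed for ALT-103-201 only".
- Listings, SAP 7.4: "All collected data will be presented in listings".
- Adverse events, SAP 8.5.3: "Any laboratory abnormality deemed clinically significant by the Investigator will be recorded as an AE".

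Nothing else in the SAP admits a higher-grade repeat when the original was already abnormal, and no worst-grade rule is given for laboratory data.

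**The concern.** The admission test has two states and the display has four or five. Admitting an abnormal repeat after a normal original is evidently meant to catch the worse of two values. On a graded scale it does so only when the original was normal. Once the original is abnormal, a repeat can rise by one, two or three grades and still be excluded. An abnormal result is also an obvious reason to repeat a test.

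An excluded repeat is also outside the continuous summaries, so no laboratory summary table would show it. Safety is the primary objective of ALT-103-201 (SAP Section 3), and laboratory summaries are part of the interim analysis that may go to regulators (SAP 7.3). The SAP counts the other safety data at their worst: reactogenicity by maximum severity (8.5.1) and treatment-emergent events by maximum severity or strongest relationship (8.5.2). Laboratory grades are handled differently, and no reason is given.

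**Working it through.** The plan states no figure on this point, so there is none to reproduce. The check is to apply the rule to every possible pair of results.

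**Inputs**

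- Rule (SAP 7.4.6): admit the repeat if the original is normal and the repeat is abnormal.
- Display (SAP 8.5.3; Tables 14.3.3.3 to 14.3.3.5): toxicity grade, by visit.
- Group sizes (SAP Table 4-1): 15 NasoVAX subjects per dose, 45 in all.
- Assumptions: normal is coded 0; any Grade 1 or higher value counts as abnormal under the low/high flag; the scale has 3 or 4 grades, because the SAP does not name the scale used for these tables.

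**Step 1. Worsening pairs (repeat grade above original grade).** With k + 1 levels (0 to k) there are k(k + 1)/2.

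- k = 4: 4 × 5 / 2 = 10.
- k = 3: 3 × 4 / 2 = 6.

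**Step 2. Pairs admitted.** The original must be 0, so k pairs are admitted and the rest are dropped.

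| Scale | Worsening pairs | Admitted | Dropped |
|---|---|---|---|
| 0 to 4 | 10 | 4 (0→1, 0→2, 0→3, 0→4) | 6 (1→2, 1→3, 1→4, 2→3, 2→4, 3→4) |
| 0 to 3 | 6 | 3 (0→1, 0→2, 0→3) | 3 (1→2, 1→3, 2→3) |

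**Step 3. Pairs that newly reach Grade 3 or higher.** On the 0 to 4 scale there are 3 originals (0, 1, 2) × 2 repeats (3, 4) = 6. The two with original 0 are admitted and 4 are dropped (1→3, 1→4, 2→3, 2→4). On the 0 to 3 scale there are 3, of which 2 are dropped (1→3, 2→3).

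**Step 4. One example.** Day 8 ALT is Grade 1 and its repeat is Grade 3. The original is not normal, so the repeat is not admitted. Table 14.3.3.4 shows Grade 1 at Day 8, which is 3 − 1 = 2 grades below the highest value observed at that visit.

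**Step 5. Scale of one subject.** One such subject is 1/15 = 6.7% of a dose group, or 1/45 = 2.2% of all NasoVAX subjects. This illustrates what one case would mean; it does not estimate how many there will be.

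**Step 6. After the fix.** If a repeat is admitted whenever its grade exceeds the original's, all 10 of 10 pairs (or 6 of 6) are kept, and the example is tabulated as Grade 3.

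**The case against.** The case against rests on how far the defect reaches. Most of it stands as a limit, but none of it removes the core.

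- **Overall worst grade.** A reader might infer that each subject's worst grade is understated. The tables are by visit and the SAP never calls them worst-grade tables. The overall worst grade is understated only if no other tabulated visit reaches it.
- **Direction.** A reader might infer that the rule makes the vaccine look safer. The documents do not show a net direction. The same rule keeps an abnormal original when its repeat is normal or lower, and adds an abnormal repeat to a normal original; at post-dose visits both raise apparent toxicity. It also applies equally to placebo. That does not restore the dropped grades, but it rules out a one-sided claim.
- **Baseline.** Screening is the only pre-dose collection of safety laboratory samples in SAP Table 4-2, so it serves as baseline under 7.4.10. Read literally, 7.4.6 could admit an abnormal Screening repeat after a normal original, raise the baseline grade and mask a later shift. A reader might infer that this feeds every shift. It could touch only subjects with that unusual sequence, and 7.4.6 does not say that an admitted repeat redefines baseline. SAP Section 4 also says the two studies shared entry criteria, and the ALT-FLZ-401 protocol (4.2) limits Screening results to normal or Grade 1, with bilirubin Grade 2 in defined cases. If ALT-103-201 does the same, a post-dose Grade 3 would still appear as a shift. What remains is that 7.4.10 does not say which Screening result prevails.
- **Stopping rule.** One criterion in SAP Section 4 is "Occurrence of the same Grade 3 laboratory abnormality in 2 or more subjects", and a reader might infer that decisions are affected. The Safety Review Committee reviews laboratory data directly, and nothing ties stopping to the shift tables. A difference between its count and the tables is possible, but it could be traced through Listings 16.2.8.1 to 16.2.8.3.
- **Other routes.** A dropped value is listed, and it enters the adverse event tables if judged clinically significant. That second route depends on judgment, so it is only a partial safeguard.
- **Unscheduled results.** The restriction names repeated tests only. A worsening sample classed as unscheduled is not barred by it, but whether it is used is left open.
- **Precision.** A reader might express the loss through confidence limits on a Grade 3 rate. The SAP plans no interval for laboratory shifts.

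The table shells and programming notes (SAP 10.2) are a separate document and could contain a further rule. The SAP text itself does not.

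**Conclusion.** The point holds as a mismatch between rule and display. As written, SAP 7.4.6 excludes any repeat that is worse than an already abnormal original, so the shift table understates the highest grade at that visit. By count of patterns this is 6 of 10 worsening pairs on a 0 to 4 scale and 3 of 6 on a 0 to 3 scale, including Grade 1 to Grade 3 on both.

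The conclusion assumes that a Grade 1 value carries a low or high flag and that the second sample is classed as a repeat. How many subjects would be affected is unknown. The defect lies in the summary reporting of ALT-103-201; ALT-FLZ-401 has clinical laboratory tests at Screening only and no safety tables in this SAP. The documents do not support a claim of harm to subject protection, of changed stopping decisions, or of a systematic bias toward safety. It should still be corrected, because a stated rule gives a wrong grade in a safety table and the remedy is cheap.

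**What to change.** Replace the restricting sentence in SAP 7.4.6 with:

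> For post-dose visits, a valid repeat or unscheduled result assigned to a visit is used in the shift tables whenever its toxicity grade exceeds that of the original result at that visit; for baseline, the last valid result before vaccination is used.

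Keep the exclusion of repeats from the continuous summaries. The word valid prevents a faulty sample from creating a shift. The new text also settles how non-repeat unscheduled results are treated and which Screening result is the baseline.

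The cost is one SAP sentence and the matching derivation in the analysis data set. No new data are needed. The small downside is that the shift tables may show slightly higher grades.
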